10.1.1 Nursing Guidelines

1. Edema and fluid retention have been noted. Instruct patient to report any swelling or weight gain to the study team.
2. Lipid abnormalities have been reported. Monitor lipid panel as per protocol. Instruct patient on appropriate diet.
3. Monitor CBC w/diff. Instruct patients to report any signs/symptoms of infection or bleeding to the study team.
4. Eye toxicity was seen in animal models but thus far has not been noted in human subjects. Instruct patients to report any ocular symptoms immediately (i.e., sore or red eyes, difficulty with or changes in vision), as ulcerative keratitis has been seen in animal models and to a lesser extent, general eye irritation.
5. Agent may be taken with or without food.

11.0 MEASUREMENT OF EFFECT

Response and progression will be evaluated in this study using the new international criteria proposed by the revised Response Evaluation Criteria in Solid Tumors (RECIST) guidelines (version 1.1). Changes in the largest diameter (unidimensional measurement) of the tumor lesions and the short axis measurements in the case of lymph nodes are used in the RECIST guideline.

11.1 Schedule of Evaluations:

For the purposes of this study, patients should be reevaluated every 6 weeks (approximately every 2 cycles) during treatment. Of note, scans should be performed according to the Study Calendar in [Section 5.0](#). In addition to a baseline scan, confirmatory scans should also be obtained ≥ 4 weeks following initial documentation of objective response

11.2 Definitions of Measurable and Non-Measurable Disease

11.2.1 Measurable Disease

A non-nodal lesion is considered measurable if its longest diameter can be accurately measured as ≥ 2.0 cm with chest x-ray, or as ≥ 1.0 cm with CT scan, CT component of a PET/CT, or MRI.

A superficial non-nodal lesion is measurable if its longest diameter is ≥ 1.0 cm in diameter as assessed using calipers (e.g. skin nodules) or imaging. In the case of skin lesions, documentation by color photography, including a ruler to estimate the size of the lesion, is recommended.

A malignant lymph node is considered measurable if its short axis is ≥ 1.5 cm when assessed by CT scan (CT scan slice thickness recommended to be no greater than 5 mm).

Tumor lesions in a previously irradiated area are not considered measurable disease.

11.2.2 Non-Measurable Disease

All other lesions (or sites of disease) are considered non-measurable disease, including pathological nodes (those with a short axis ≥ 1.0 to < 1.5 cm). Bone lesions, leptomeningeal disease, ascites, pleural/pericardial effusions, lymphangitis cutis/pulmonis, inflammatory breast disease, and abdominal masses (not followed by CT or MRI), are considered as non-measurable as well.

Note: ‘Cystic lesions’ thought to represent cystic metastases can be considered as measurable lesions, if they meet the definition of measurability described above. However, if non-cystic lesions are present in the same patient, these are preferred for selection as target lesions. In addition, lymph nodes that have a short axis < 1.0 cm are considered non-pathological (i.e., normal) and should not be recorded or followed.

11.3 Guidelines for Evaluation of Measurable Disease

11.3.1 Measurement Methods:

- All measurements should be recorded in metric notation (i.e., decimal fractions of centimeters) using a ruler or calipers.
- The same method of assessment and the same technique must be used to characterize each identified and reported lesion at baseline and during follow-up. For patients having only lesions measuring at least 1 cm to less than 2 cm must use CT imaging for both pre- and post-treatment tumor assessments.
- Imaging-based evaluation is preferred to evaluation by clinical examination when both methods have been used at the same evaluation to assess the antitumor effect of a treatment.

11.3.2 Acceptable Modalities for Measurable Disease:

- **Conventional CT and MRI:** This guideline has defined measurability of lesions on CT scan based on the assumption that CT slice thickness is 5 mm or less. If CT scans have slice thickness greater than 5 mm, the minimum size for a measurable lesion should be twice the slice thickness.
As with CT, if an MRI is performed, the technical specifications of the scanning sequences used should be optimized for the evaluation of the type and site of disease. The lesions should be measured on the same pulse sequence. Ideally, the same type of scanner should be used and the image acquisition protocol should be followed as closely as possible to prior scans. Body scans should be performed with breath-hold scanning techniques, if possible.
- **PET-CT:** If the site can document that the CT performed as part of a PET-CT is of identical diagnostic quality to a diagnostic CT (with IV and oral contrast), then the CT portion of the PET-CT can be used for RECIST measurements and can be used interchangeably with conventional CT in accurately measuring cancer lesions over time.
- **Chest X-ray:** Lesions on chest x-ray are acceptable as measurable lesions when they are clearly defined and surrounded by aerated lung. However, CT scans are preferable.
- **Physical Examination:** For superficial non-nodal lesions, physical examination is acceptable, but imaging is preferable, if both can be done. In the case of skin lesions,

documentation by color photography, including a ruler to estimate the size of the lesion, is recommended.

- **FDG-PET:** FDG-PET scanning is allowed to complement CT scanning in assessment of progressive disease (PD) and particularly possible 'new' disease. A 'positive' FDG-PET scanned lesion is defined as one which is FDG avid with an uptake greater than twice that of the surrounding tissue on the attenuation corrected image; otherwise, an FDG-PET scanned lesion is considered 'negative.' New lesions on the basis of FDG-PET imaging can be identified according to the following algorithm:
 - a. Negative FDG-PET at baseline with a positive FDG-PET at follow-up is a sign of PD based on a new lesion.
 - b. No FDG-PET at baseline and a positive FDG-PET at follow-up:
 - 1) If the positive FDG-PET at follow-up corresponds to a new site of disease confirmed by CT, this is PD.
 - 2) If the positive FDG-PET at follow-up is not confirmed as a new site of disease on CT at the same evaluation, additional follow-up CT scans (i.e., additional follow-up scans at least 4 weeks later) are needed to determine if there is truly progression occurring at that site. In this situation, the date of PD will be the date of the initial abnormal PDG-PET scan.
 - 3) If the positive FDG-PET at follow-up corresponds to a pre-existing site of disease on CT that is not progressing on the basis of the anatomic images, it is not classified as PD.

11.3.3 Measurement at Follow-up Evaluation:

- A subsequent scan must be obtained ≥ 4 weeks following initial documentation of an objective status of either complete response (CR) or partial response (PR).
- In the case of stable disease (SD), follow-up measurements must have met the SD criteria at least once after study entry at a minimum interval 6 weeks (see [Section 11.4.4](#)).
- The cytological confirmation of the neoplastic origin of any effusion that appears or worsens during treatment when the measurable tumor has met criteria for response or stable disease is mandatory to differentiate between response or stable disease (an effusion may be a side effect of the treatment) and progressive disease.
- Cytologic and histologic techniques can be used to differentiate between PR and CR in rare cases

11.4 Measurement of Treatment/Intervention Effect

11.4.1 Target Lesions & Target Lymph Nodes

- Measurable lesions (as defined in [Section 11.2.1](#)) up to a maximum of 5, representative of all involved organs, should be identified as "Target Lesions" and recorded and measured at baseline. These lesions can be non-nodal or nodal (as defined in 11.2.1), where no more than 2 lesions are from the same organ and no more than 2 malignant nodal lesions are selected.

Note: If fewer than 5 target lesions and target lymph nodes are identified (as there often will be), there is no reason to perform additional studies beyond those specified in the protocol to discover new lesions.

- Target lesions and target lymph nodes should be selected on the basis of their size, be representative of all involved sites of disease, but in addition should be those that lend themselves to reproducible repeated measurements. It may be the case that, on occasion, the largest lesion (or malignant lymph node) does not lend itself to reproducible measurements in which circumstance the next largest lesion (or malignant lymph node) which can be measured reproducibly should be selected.
- **Baseline Sum of Dimensions (BSD):** A sum of the longest diameter for all target lesions plus the sum of the short axis of all the target lymph nodes will be calculated and reported as the baseline sum of dimensions (BSD). The BSD will be used as reference to further characterize any objective tumor response in the measurable dimension of the disease.
- **Post-Baseline Sum of the Dimensions (PBSD):** A sum of the longest diameter for all target lesions plus the sum of the short axis of all the target lymph nodes will be calculated and reported as the post-baseline sum of dimensions (PBSD). If the radiologist is able to provide an actual measure for the target lesion (or target lymph node), that should be recorded, even if it is below 0.5 cm. If the target lesion (or target lymph node) is believed to be present and is faintly seen but too small to measure, a default value of 0.5 cm should be assigned. If it is the opinion of the radiologist that the target lesion or target lymph node has likely disappeared, the measurement should be recorded as 0 cm.
- **The minimum sum of the dimensions (MSD)** is the minimum of the BSD and the PBSD.

11.4.2 Non-Target Lesions & Non-Target Lymph Nodes

Non-measurable sites of disease ([Section 11.2.2](#)) are classified as non-target lesions or non-target lymph nodes and should also be recorded at baseline. These lesions and lymph nodes should be followed in accord with 11.4.3.3.

11.4.3 Response Criteria

- 11.4.3.1** All target lesions and target lymph nodes followed by CT/MRI/PET-CT/Chest X-ray/physical examination must be measured on re-evaluation at evaluation times specified in [Section 11.1](#). Specifically, a change in objective status to either a PR or CR cannot be done without re-measuring target lesions and target lymph nodes.

Note: Non-target lesions and non-target lymph nodes should be evaluated at each assessment, especially in the case of first response or confirmation of response. In selected circumstances, certain non-target organs may be evaluated less frequently. For example, bone scans may need to be repeated only when complete response is identified in target disease or when progression in bone is suspected.

11.4.3.2 Evaluation of Target Lesions

- **Complete Response (CR):** All of the following must be true:
 - a. Disappearance of all target lesions.
 - b. Each target lymph node must have reduction in short axis to < 1.0 cm.
- **Partial Response (PR):** At least a 30% decrease in PBSD (sum of the longest diameter for all target lesions plus the sum of the short axis of all the target lymph nodes at current evaluation) taking as reference the BSD (see [Section 11.4.1](#)).

- **Progression (PD):** At least one of the following must be true:
 - a. At least one new malignant lesion, which also includes any lymph node that was normal at baseline (< 1.0 cm short axis) and increased to \geq 1.0 cm short axis during follow-up.
 - b. At least a 20% increase in PBSD (sum of the longest diameter for all target lesions plus the sum of the short axis of all the target lymph nodes at current evaluation) taking as reference the MSD ([Section 11.4.1](#)). In addition, the PBSD must also demonstrate an absolute increase of at least 0.5 cm from the MSD.
 - c. See [Section 11.3.2](#) for details in regards to the requirements for PD via FDG-PET imaging.
- **Stable Disease (SD):** Neither sufficient shrinkage to qualify for PR, nor sufficient increase to qualify for PD taking as reference the MSD.

11.4.3.3 Evaluation of Non-Target Lesions & Non-target Lymph Nodes

- **Complete Response (CR):** All of the following must be true:
 - a. Disappearance of all non-target lesions.
 - b. Each non-target lymph node must have a reduction in short axis to <1.0 cm.
- **Non-CR/Non-PD:** Persistence of one or more non-target lesions or non-target lymph nodes.
- **Progression (PD):** At least one of the following must be true:
 - a. At least one new malignant lesion, which also includes any lymph node that was normal at baseline (< 1.0 cm short axis) and increased to \geq 1.0 cm short axis during follow-up.
 - b. Unequivocal progression of existing non-target lesions and non-target lymph nodes. (NOTE: Unequivocal progression should not normally trump target lesion and target lymph node status. It must be representative of overall disease status change.)
 - c. See [Section 11.3.2](#) for details in regards to the requirements for PD via FDG-PET imaging.

11.4.4 Overall Objective Status

The overall objective status for an evaluation is determined by combining the patient's status on target lesions, target lymph nodes, non-target lesions, non-target lymph nodes, and new disease as defined in the following table:

Target Lesions & Target Lymph Nodes	Non-Target Lesions & Non-Target Lymph Nodes	New Sites of Disease	Overall Objective Status
CR	CR	No	CR
CR	Non-CR/Non-PD	No	PR
PR	CR Non-CR/Non-PD	No	PR
CR/PR	Not All Evaluated*	No	PR**
SD	CR Non-CR/Non-PD Not All Evaluated*	No	SD

Target Lesions & Target Lymph Nodes	Non-Target Lesions & Non-Target Lymph Nodes	New Sites of Disease	Overall Objective Status
Not all Evaluated	CR Non-CR/Non-PD Not All Evaluated*	No	Not Evaluated (NE)
PD	Unequivocal PD CR Non-CR/Non-PD Not All Evaluated*	Yes or No	PD
CR/PR/SD/PD/Not all Evaluated	Unequivocal PD	Yes or No	PD
CR/PR/SD/PD/Not all Evaluated	CR Non-CR/Non-PD Not All Evaluated*	Yes	PD

* See [Section 11.4.3.1](#)

11.4.5 Symptomatic Deterioration: Patients with global deterioration of health status requiring discontinuation of treatment without objective evidence of disease progression at that time, and not either related to study treatment or other medical conditions, should be reported as PD due to “symptomatic deterioration.” Every effort should be made to document the objective progression even after discontinuation of treatment due to symptomatic deterioration.

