 - 2 For women of childbearing potential (see [Section 3.3](#)). Must be done \leq 7 days prior to registration and \leq 7 days prior to re-registration at crossover.
 - 3 See [Sections 4.5](#) and [6.1](#).
 - 4 Baseline scans can include either: 1) a CT, spiral CT, or MRI, or 2) an FDG-PET scan and diagnostic CT performed with both IV and oral contrast, and the CT acquired with 5 mm or less slice thickness. If a bone scan is used for baseline scan, please note in ECRF, but bone scans are not mandatory. Documentation (radiologic and pathology report and clinic note) of the diagnosis scan must be submitted.
 - 5 Fasting triglycerides and total cholesterol will be done on Day 1 of Cycles 3 and 6 (+/- 7 days).
- A Every 6 weeks (approximately every 2 cycles) through 24 weeks, and then every 12 weeks (approximately every 4 cycles) after week 24 until evidence of progression or relapse. Scans may be done up to 7 days prior to beginning a cycle. Confirmatory scans should also be obtained at least 4 weeks following documentation of objective response (see [Section 11.0](#)).
If the baseline scans were a CT or MRI and bone scan, follow-up bone scans are required only for patients with bone metastases as the only site of evaluable disease, and are optional for other patients. **Response assessment should include assessment of all sites of disease and use the same imaging method as was used at baseline.** Documentation (radiologic and clinic note) must be provided at progression of disease.

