13.2 Primary Endpoint and Study Design

The primary endpoint for this study will assess the confirmed response rate (by RECIST 1.1) of efatutazone in patients with advanced, unresectable, or metastatic myxoid liposarcoma who have received at least one prior systemic therapy. Any confirmed response that occurs during the first 8 cycles of treatment will count as a success (24 weeks). Per RECIST 1.1, responses need to be confirmed (2 consecutive responses at least 4 weeks apart) to count as a response (see Section 11). All eligible patients who are registered and start treatment will be evaluable for response. A Simon's optimal two-stage design will be utilized (see below). This design has 80% power to detect an improvement in the confirmed response rate from 5% to 20%, with a significance level of 0.10. See design details below:

Interim Analysis: Enroll 9 eligible patients (need 6 additional patients after design change to single arm trial). If at least 1 confirmed response is observed in the first 9 eligible patients, we will continue the study to a full accrual of 24 eligible patients. Otherwise, the study will be permanently closed due to lack of efficacy. The study will remain open during the interim analysis phase due to slow projected accrual rate and minimal expected toxicity.

Final Analysis: If the trial is a success during the interim analysis, we will enroll another 15 eligible patients (24 eligible total). If at least 3 confirmed responses are observed in the first 24 eligible patients (13%), the treatment will be considered worthy of further investigation. Otherwise, the study will be permanently closed due to lack of efficacy.

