13.3 Secondary Endpoints

The following endpoints will be assessed: progression-free survival, overall survival, and adverse events. All patients who meet the eligibility criteria, and sign the consent form will be considered evaluable for these endpoints.

Progression-Free Survival: Progression-free survival (PFS) is defined as the time from study entry to the first of either disease progression or death from any cause, where disease progression will be determined based on RECIST 1.1 criteria. PFS will be estimated using the Kaplan-Meier method.

Overall Survival: Overall survival (OS) is defined as the time from study entry to death from any cause. OS will be estimated using the Kaplan-Meier method.

Adverse events: The maximum grade for each type of adverse event will be summarized using CTCAE version 4.0. The frequency and percentage of grade 3+ adverse events will be estimated.

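### The overall-status table has no rule for a scan with an unread target lesion whose measured lesions alone already meet the progression criterion, and 13.2 does not say whether a not-evaluable scan breaks two consecutive responses

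*Combined protocol and SAP*

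**What the plan says.** **Progression in target lesions.** Section 11.4.3.2, criterion (b), requires "At least a 20% increase in PBSD (sum of the longest diameter for all target lesions" plus the nodal short axes, measured against the MSD. It adds that "the PBSD must also demonstrate an absolute increase of at least 0.5 cm from the MSD". Section 11.4.1 defines the post-baseline sum (PBSD) over all target lesions and nodes and gives no rule for a partial sum.

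**Overall status.** The Section 11.4.4 table treats progression and incomplete evaluation as separate target statuses. With incomplete targets, non-targets not progressing and no new site, the result is "Not Evaluated (NE". Two other rows list the target status as "CR/PR/SD/PD/Not all Evaluated" and return PD, one because of unequivocal non-target progression and one because of a new site.

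**Use in the endpoints.** Section 13.3 defines PFS as running to progression or death, "where disease progression will be determined based on RECIST 1.1 criteria", with no rule for NE scans. Section 13.2 states that "responses need to be confirmed (2 consecutive responses at least 4 weeks apart) to count as a response" and counts only the first 8 cycles (24 weeks). Footnote A of the Study Calendar sets scans every 6 weeks through week 24, "then every 12 weeks (approximately every 4 cycles) after week 24 until evidence of progression or relapse".

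**The concern.** A lesion diameter cannot be negative. If the lesions that were read already exceed the progression threshold on their own, the full sum exceeds it too, and the unread lesion is irrelevant. The table's NE row nevertheless covers this scan. Two coders could then give it different statuses, and the literal one misses a progression that the data already establish.

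The error in PFS has one direction: a progression coded NE is dated later or missed, never earlier. A single-arm Kaplan-Meier estimate has no comparator in which the same error could cancel.

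The same status touches the primary endpoint differently. If NE interrupts two consecutive responses, a responder with one unreadable lesion at the middle scan may not count, and the decision rests on 3 responses in 24 patients.

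**Working it through.** **1. The plan's own design figure.** Inputs from 13.2: continue with at least 1 of 9 responses, succeed with at least 3 of 24, rates 5% and 20%. The exact two-stage binomial gives a type I error of 0.093 and power of 0.805, in line with the stated 0.10 and 80%. The design stands.

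**2. When a partial sum proves progression.** Let S be the sum of the lesions read. The full PBSD is at least S. So if S ≥ 1.2 × MSD and S ≥ MSD + 0.5 cm, criterion (b) is met. Illustration with assumed sizes: MSD = 5 + 4 + 3 = 12 cm, threshold 1.2 × 12 = 14.4 cm. Two lesions read at 8 + 7 = 15 cm exceed it, by 3 cm over MSD, with the third unread. The NE row still fits this scan.

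**3. How much growth this takes.** With m equal lesions at the MSD (assumption) and one unread, the others must grow by 1.2 × m/(m − 1) − 1:

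| Target lesions | Growth needed in those read |
|---|---|
| 2 | 140% |
| 3 | 80% |
| 4 | 60% |
| 5 | 50% |

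With a single target the case cannot arise. If the unread lesion is a smaller share s of the MSD, the requirement is 1.2/(1 − s) − 1; for s = 10% that is 33%.

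**4. Shift in the progression date.** Scheduled scans fall at weeks 6, 12, 18, 24, 36, 48 and so on. If the scan is coded NE and the next shows progression, the date moves by 6 weeks for scans at weeks 6, 12 and 18, and by 12 weeks for scans at week 24 or later, before visit windows.

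**5. Ceiling on patients affected.** The documents give no frequency. Assuming 5% to 10% of scans miss a target lesion and half of progressions come from target growth: 24 × 0.05 × 0.5 = 0.6 and 24 × 0.10 × 0.5 = 1.2 patients. This supposes that the measured lesions always suffice alone, which step 3 shows they usually will not.

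**6. Response side.** Response at week 12, NE at week 18, response at week 24 leaves no later scheduled scan in the 24-week window. At a true 20% rate:

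- P(exactly 3 of 24) = C(24,3) × 0.2³ × 0.8²¹ = 0.149.
- P(at least 1 of those 3 is in the first 9) = 1 − C(15,3)/C(24,3) = 1 − 455/2024 = 0.775.
- Product: 0.149 × 0.775 = 0.116.
- Chance that at least one of the three is lost, at 5% or 10% each: 0.116 × (1 − 0.95³) = 1.7%; 0.116 × (1 − 0.90³) = 3.1%.

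That covers the final boundary with exactly 3 responders. To include the 1-of-9 interim threshold and multiple losses, apply the effective rate to the whole design: 0.20 × 0.95 = 0.19 gives power 0.777, and 0.20 × 0.90 = 0.18 gives 0.745, against 0.805. The loss is 2.8 to 6.0 percentage points. Both calculations assume that a patient whose confirmation is missed never confirms later, so they are upper figures.

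**The case against.** The strongest reply is that the table does not force NE. Criterion (b) is an inequality, "At least a 20% increase in PBSD", and in the case described it is certainly met. A reader may therefore set the target status to PD and use the PD row. Section 11.4.3.1 asks for all targets to be measured, but the only changes it expressly bars without re-measurement are to PR and CR. This stands as a permissible reading. It does not remove the gap, because PBSD is defined only over the full set and no precedence is stated.

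A reader might also infer more than the documents support:

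- **That any scan with an unread target is NE.** Two rows return PD despite unread targets.
- **That treatment continues past proven progression.** No section says so. Section 7.0 ties continuation at reimaging to the absence of evidence of progression, but also says treatment runs until progression or unacceptable toxicity. Section 12.1.1 lists CR, PR and SD as continuing and omits NE. The documents leave the point open.
- **That median PFS is inflated by 25% to 42%.** Those ratios set one patient's 6 weeks (6 × 7/30.44 = 1.38 months) against the 5.5- and 3.3-month medians quoted in the background. A handful of shifted dates at most would not move a group median by that proportion.
- **That 11.6% is an error rate.** It is only the chance of sitting at the 3-of-24 boundary.

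On the response side, response, NE, response, response confirms on its last two scans. Section 11.3.3 asks only for a subsequent scan at least 4 weeks later, which is looser than the wording in 13.2. Both points reduce the loss; neither settles the week 12, 18, 24 sequence.

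**Conclusion.** The gap is real and small. Followed literally, the NE row gives the wrong status to a scan whose measured lesions already satisfy criterion (b). The consequence, if NE is coded and the next scan shows progression, is a PFS date one scan interval late. It affects a secondary, descriptive estimate with no hypothesis or threshold attached, and always lengthens it. The frequency is unknown; the growth required suggests rare cases.

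The undefined word in the primary endpoint matters slightly more, because it can touch a decision. On an assumed 5% to 10% missed-lesion rate, the chance of a reversed final decision at the 3-of-24 boundary is roughly 2% to 3%. With the interim threshold included, the upper bound on lost power is about 3 to 6 points. The Simon design itself needs no change, and the documents do not establish that patients are treated beyond proven progression.

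**What to change.** 1. In Section 11.4.4, add to the incomplete-target row: *NE, unless the evaluated target lesions alone already meet PD criterion (b) of 11.4.3.2; then the status is PD on that date.*
2. In Section 13.2, state that an NE evaluation between two responses does not break the consecutive requirement, while an SD or PD evaluation does. Make this change together with the first, so that a scan that proves progression cannot be bridged as NE.
3. Reconcile Sections 7.0 and 12.1 on what follows an NE scan. This is for the study team; no clinical rule is proposed here.

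The statistical changes cost one table note and one sentence, with no new scans, data or patients. Where the note applies, PFS will be slightly shorter and correctly dated.
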